### Change and percent change from baseline

Change from baseline will be calculated as follows:

- Post-baseline value – baseline value

Percent change from baseline will be calculated as follows:

- $[(\text{Post-baseline value} - \text{baseline value}) / \text{baseline value}] \times 100\%$

Change and percent change from baseline will only be calculated and summarized for participants with both baseline and post-baseline values.

Change and percent change from Month 6 re-baseline will be calculated in a similar fashion using the above formulas where ‘baseline value’ is replaced with ‘Month 6 re-baseline value’ (i.e., Month 6 value) and ‘Post-baseline value’ is replaced with ‘Post-Month 6 value’.

## 2.2 Analysis sets

The Full Analysis Set (FAS) will include all enrolled participants that received any study drug.

The Safety Analysis Set (SAF) will be the same as the FAS.

The Healthy Control Analysis Set (HCAS) will include all enrolled healthy control participants. This analysis set will be used in the analysis of data collected from healthy control participants.

The modified FAS (mFAS) will include all participants in the FAS except for those who discontinued treatment prematurely prior to Month 18 for reasons other than lack of efficacy or death, or those who completed their Month 18 visit but missed relapse/EDSS/MRI (Gd+ or

new/enlarging T2 lesions) at Month 6, 12 or 18, unless they showed disease activity (i.e., MRI activity after Month 6 through 18 or relapse/3-month clinical disability progression between Months 6 and 18). The mFAS will be used for NEDA-3, NEDA clinical and NEDA radiological efficacy analyses.

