2.2 Secondary estimands

Not applicable.

3 Study design

This study is an open-label, multi-center, prospective eighteen-month study in a minimum of

118 MS patients with early RRMS (defined as within 6 months of diagnosis of clinically

definite RRMS) and who are disease modifying therapy (DMT) treatment naïve. RRMS patients will be benchmarked against age- and sex-matched healthy controls (n=50) for select secondary [REDACTED]. A screening period of 4 weeks will be used to assess eligibility and the assessment to address the primary objective will be performed at the end of the maintenance period (Month 18). There will be one interim analysis after the last participant completes his/her Month 18 (primary analysis time point) visit. Participants who complete the treatment period or who prematurely discontinue study drug and the study, and do not continue on any MS DMT, will undergo a safety evaluation 100 days following last dose of study treatment (captured only in source documents and only for ofatumumab treated participants), and will be discharged from the study if they choose to not be included in the optional extension portion of the trial for an additional 12 months (up to 30 months total in trial). Healthy control participants will not have a safety evaluation post end of study. Additional efficacy and safety assessments will be evaluated during the optional open-label extension to further elucidate the long-term clinical and radiological effects of ofatumumab (Figure 3-1). Of note, MRI data will be re-baselined at month 6 to account for treatment-related pseudo atrophy.

[figure not shown]
Eligible participants with RRMS will receive ofatumumab 20mg subcutaneous doses at Baseline/Week 0 (Day 1), followed by Week 1 (Day 7), Week 2 (Day 14) and then every month thereafter, beginning at Week 4 (Month 1) until Month 18 (see Figure 3-1). Additional efficacy and safety assessments will be evaluated up to 30 months, necessitating ofatumumab monotherapy over the course of up to 30 months. Ofatumumab will be administered according to the United States Prescribing Information (USPI). RRMS patients must remain on ofatumumab monotherapy to remain in the trial, with no DMT switching or combination DMT therapy allowed. Healthy controls will not be given a therapy.

Assessments will be performed per the assessment schedule found in Table 8-1.

Figure 3-1 Study design

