6.1.4 Treatment duration

The planned duration of treatment is 18 months and participants will continue on ofatumumab treatment arm for 18 months. Once a participant is started on ofatumumab, they must remain on ofatumumab throughout the duration of the study and switching to a different DMT therapy will not be permitted. Participants may be discontinued from treatment earlier due to unacceptable adverse events, disease progression and/or at the discretion of the Investigator or the participant. Additional efficacy and safety assessments will be evaluated during an optional 12-month open-label extension, necessitating ofatumumab monotherapy over the course of up to 30 months in patients that choose to enter the extension.

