6.2.2 Prohibited medication

Use of the treatments displayed in [Table 6-1](#) is NOT allowed in combination with study drug, due to increased risk of immunosuppression and confounding of efficacy evaluations.

Exclusionary medications for study eligibility are listed in the exclusion criteria ([Section 5.2](#)). Use of excluded medications is not allowed while the participant is on study medication.

Table 6-3 Prohibited medication

Medication	Action taken
Immunosuppressive/chemotherapeutic medications (including herbal) or procedures, including but not limited to cyclosporine, azathioprine, leflunomide, methotrexate, cyclophosphamide, mitoxantrone, lymphoid irradiation and hematopoietic stem cell transplantation	Discontinue study drug, increase vigilance regarding infections. NOTE: Restarting study drug in participants exposed to these medications is not permitted.
Monoclonal antibodies targeting the immune system, including but not limited to natalizumab, alemtuzumab, daclizumab ocrelizumab and rituximab and B-cell depleting agents under investigation, such as but not limited to ublituximab and obinutuzumab	Discontinue study drug, increase vigilance regarding infections. NOTE: Restarting study drug after exposure to B-cell depleting agents is not permitted. For others only after consultation with Novartis.
Any other immunomodulatory or disease-modifying MS treatment, including but not limited to fingolimod, interferon beta, glatiramer acetate, dimethyl fumarate, intravenous immunoglobulin, plasmapheresis or systemic corticosteroids (except for when given for MS relapse treatment as defined in Section 6.2.3)	Discontinue study drug, increase vigilance regarding infections. NOTE: Restarting study drug in participants exposed to these medications is not permitted.
Administration of any live or live-attenuated (does not apply to non-live, inactivated, mRNA, adenovirus vector vaccines) vaccine (including for measles) is prohibited while participants are exposed to study drug (long lasting effects of the study drugs should be taken into consideration)	They may be administered 4 weeks prior to first administration of ofatumumab in the study or when participants are no longer exposed to study drug with documented B cell repletion. Consider risk/benefit and follow local labels.

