9.1 Discontinuation from study treatment and from study

9.1.1 Discontinuation from study treatment

Discontinuation of study treatment for a participant occurs when study treatment is permanently stopped for any reason (prior to the planned completion of study drug administration, if any) and can be initiated by either the participant or the investigator.

The investigator must discontinue study treatment for a given participant if, he/she believes that continuation would negatively impact the participant's well-being.

Discontinuation from study treatment is required under the following circumstances:

- Participant/guardian decision ([Section 9.2](#))
 - Pregnancy ([Section 8.4.2](#) and [Section 10.1.4](#))
 - Use of prohibited treatment as per recommendations in the prohibited treatment section ([Section 6.2.2](#))
 - Diagnosis of PML ([Section 16.1.1](#))
 - Hypersensitivity to the study drug
 - Protocol violation that results in a significant risk to the patient's safety
 - Emergence of certain adverse events, such as malignancy (except successfully treated basal cell carcinoma, *in situ* squamous cell carcinoma and *in situ* carcinoma of cervix of uterus), liver failure or, serious chronic infection (such as HIV)
- 

- Laboratory abnormalities requiring the action of study drug discontinuation as defined in [Appendix 16.1](#) and abnormal test procedure as defined in [Appendix 16.1.3](#)
 - Any laboratory abnormalities that in the judgment of the Investigator, taking into consideration the participant's overall status, prevents the participant from continuing participation in the study
- Any situation in which continued study participation might result in a safety risk to the participant
- Non-compliance with study drug or study procedures

If discontinuation from study treatment occurs, the investigator should make a reasonable effort to understand the primary reason for the participant's discontinuation from study treatment and record this information.

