### 1.2.1 Primary estimand(s)

The estimand is the precise description of the treatment effect and reflects strategies to address events occurring during the trial conduct which could impact the interpretation of the trial results (e.g., premature discontinuation of treatment).

The primary clinical question of interest is: will treatment with ofatumumab allow young and very early RRMS patients to achieve NEDA-3 at 18 months?

The justification for the primary estimand is that it will capture the effect of ofatumumab on shutting down MS inflammatory and associated clinical disease activity within the central nervous system (CNS) in a RRMS population that is at first diagnosis.

The primary estimand is described by the following attributes:

- **Population:** Defined through appropriate inclusion/exclusion criteria to reflect the targeted population. Young adult and very early RRMS (defined as within 6 months of diagnosis of clinically definite RRMS) patients that are DMT treatment naïve.
- **Variable:** NEDA-3 (relapse-free, clinical disability progression-free, MRI activity-free) in Months 6 to 18 (yes/no)
- **Treatment of interest:** An initial dose regimen consisting of doses administered at Baseline/Week 0 (Day 1), followed by Week 1 (Day 7), Week 2 (Day 14), and then every month thereafter, beginning at Week 4 (Month 1) until Month 18 (see [Figure 1](#)). All doses of ofatumumab will be given subcutaneously via an auto-injector at a dose of 20 mg. Healthy controls will be used for comparison purposes and will not receive study treatment.
- **Intercurrent event:** Treatment discontinuation due to lack of efficacy or death

- **Summary measure:** Proportion of participants achieving NEDA-3 in Months 6 to 18

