### 2.5.3 Handling of intercurrent events

Handling of treatment discontinuations will follow composite variable strategy. For treatment discontinuation prior to Month 18 due to lack of efficacy or death, NEDA-3 and associated endpoints will be considered as “non-response”; if treatment discontinuation prior to Month 18 is due to reasons other than lack of efficacy or death, or if the Month 18 visit was completed but relapse/EDSS/MRI (Gd+ or new/enlarging T2 lesions) was missed at Month 6, 12 or 18, and disease activity was not shown (i.e., MRI activity after Month 6 through 18 or relapse/3-month clinical disability progression between Months 6 and 18), the participant will be excluded from mFAS for all NEDA-3 and associated endpoints efficacy analyses and thusly out of scope for intercurrent events handling; the rest of the participants had disease activities in Months 6 to 18, and NEDA-3 and associated endpoints for those participants will be considered as “non-response”.

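### Stopping for disease progression is not mapped to lack of efficacy, so a stopper with no qualifying Month 6 to 18 activity on record leaves the NEDA-3 denominator instead of counting as a failure

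*SAP*

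**What the plan says.** SAP 2.5.2 analyses NEDA-3 in the mFAS. SAP 2.2 builds the mFAS by taking out of the FAS, among others, participants who "discontinued treatment prematurely prior to Month 18 for reasons other than lack of efficacy or death". The exclusion has an exception: "unless they showed disease activity (i.e., MRI activity after Month 6 through 18", or a relapse or 3-month progression in that period.

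SAP 1.2.1 and 2.5.1 define the intercurrent event as "Treatment discontinuation due to lack of efficacy or death". SAP 2.5.3 scores that event as non-response whenever it occurs before Month 18, with no earliest date. It then excludes stoppers for other reasons in whom no activity was shown. Of those left it says that "the rest of the participants had disease activities in Months 6 to 18", and it scores them as non-response too.

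The protocol uses other words for stopping. Section 6.1.4 says: "Participants may be discontinued from treatment earlier due to unacceptable adverse events, disease progression and/or at the discretion of the Investigator or the participant". Section 9.1.1 requires stopping for, among other things, "Use of prohibited treatment as per recommendations in the prohibited treatment section", and Table 6-3 in section 6.2.2 includes "Any other immunomodulatory or disease-modifying MS treatment" in that class. Section 3 adds that "RRMS patients must remain on ofatumumab monotherapy to remain in the trial". Neither document says which recorded reasons count as lack of efficacy.

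**The concern.** The SAP adopts a composite strategy: stopping because treatment has failed is itself a bad outcome. For that to work, the rule must recognise every stop made because the disease is active. Here it recognises one label, and that label does not appear among the participant-level stopping reasons in the readable text of Protocol 6.1.4 or 9.1.1. Protocol 10.1.1 (causality of adverse events) names lack of efficacy and progression of the illness as alternatives, so a programmer cannot assume that they are synonyms. Protocol 9.1.1 asks for one primary reason, so one entry can decide whether a participant is a failure or is not counted.

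The primary result is a single proportion with an exact confidence interval, no hypothesis test (SAP 5.4.1) and no sensitivity analysis (SAP 2.5.5). Who is in the denominator therefore matters a good deal. Failures that drop out through this gap can only raise the reported proportion.

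**Working it through.** **1. The plan's own figures (SAP 3.1).** Inputs: n = 100, expected proportions 80% and 85%, 15% drop-out.
- Half-width = 1.96 × √(p(1−p)/100) = 7.84% at p = 0.80 and 7.00% at p = 0.85. These match the stated 7.8% and 7.0%.
- Enrolment = 100/(1 − 0.15) = 117.6, rounded up to 118, as stated. The allowance is 118 − 100 = 18 participants for drop-out of every kind.

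**2. The rule applied to stops before Month 18.**

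| What is on record | Labelled lack of efficacy | Labelled disease progression |
|---|---|---|
| Confirmed relapse, 3-month-confirmed EDSS progression or MRI activity in Months 6 to 18 | Failure | Failure |
| Relapse at Month 4, stop at Month 5 | Failure | Removed from mFAS |
| EDSS rise meeting Table 7 at Month 9, stop before confirmation, no confirmed relapse, no MRI activity after Month 6 | Failure | Removed from mFAS |

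The label changes nothing in the first row and decides the outcome in the other two.

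**3. Why worsening can stay unconfirmed.** SAP 2.5.1 requires the EDSS rise to be sustained and then confirmed at a scheduled visit at least 3 months after onset. After Month 6, the scheduled EDSS time points up to the primary analysis are Months 12 and 18 (SAP Table 3). An End of Study visit within 7 days of leaving (Protocol section 3) cannot confirm a recent rise. SAP 2.5.1 waives confirmation only for the Month 18 assessment. Once treatment has stopped, the minimum data in Protocol 9.1.1 are new treatments and adverse events, and a participant who changes therapy cannot stay in the trial.

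**4. Size.** Let r be the successes among 100 in the mFAS and k the removed stoppers restored as failures. The proportion becomes r/(100 + k). The documents give no value for k, so it is an assumption. Its range is 0 to 18, where 18 would mean that the whole drop-out allowance was of this kind. Limits are Clopper-Pearson 95%.

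| k | r = 80 | r = 85 |
|---|---|---|
| 0 | 80.0% (70.8 to 87.3) | 85.0% (76.5 to 91.4) |
| 1 | 79.2% (70.0 to 86.6) | 84.2% (75.6 to 90.7) |
| 3 | 77.7% (68.4 to 85.3) | 82.5% (73.8 to 89.3) |
| 5 | 76.2% (66.9 to 84.0) | 81.0% (72.1 to 88.0) |
| 18 | 67.8% (58.6 to 76.1) | 72.0% (63.0 to 79.9) |

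One case costs 80.0 − 79.2 = 0.8 points. Five cost 80.0 − 76.2 = 3.8 points, about half the planned half-width of 7.8.

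**5. What the supplementary analyses show.** The non-response analysis on the FAS scores every participant with incomplete data as a failure. With 118 treated, 80 successes and 18 incomplete, it gives 80/118 = 67.8%, the k = 18 row. That is a lower bound, but it mixes in unrelated drop-out. The completer analysis requires the Month 6 and Month 18 visits, so a participant who left before Month 18 is missing there as well.

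**The case against.** The strongest reply is that the gap is small and partly closed already.

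- **Recorded activity counts under any label.** This is correct. A reader who stops at the words quoted from SAP 2.2 might infer that every stop for active disease outside the lack-of-efficacy label leaves the denominator. The exception that follows, and SAP 2.5.3, rule that out.
- **Early leavers are examined.** The End of Study visit is mandatory (Protocol 9.3), Table 8-1 has MRI in that column, and Protocol 9.1.1 asks those who stop treatment to return where possible. A relapse is confirmed by an EDSS rise of only 0.5 (Protocol 8.3.1). These steps will catch many cases, but they do not reach stops before Month 6 or a rise that is too recent to confirm.
- **Activity before Month 6 is outside the endpoint.** True: a participant with a Month 4 relapse who continues can still achieve NEDA-3. But SAP 2.5.3 fails the early stopper under one label and removes the same participant under another. The inconsistency remains whichever treatment is preferred.
- **The disposition form is not in the documents.** It may offer lack of efficacy, and sites may use it for progression. That would reduce the number of cases, but the SAP would still not say how a recorded reason of disease progression is handled.
- **Switching therapy.** It is tempting to infer that anyone who starts another MS therapy after stopping should be a failure. The documents do not support this. Protocol 6.1.5 sends participants who stop early, including for adverse events, to their own physician for other treatment without delay. Section 6.2.2 bars the listed drugs in combination with study drug, so it is only an assumption that a switch made after stopping would be recorded as prohibited treatment.

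**Conclusion.** The point stands in a limited form. Two groups are affected: participants who stop for disease progression or relapse before Month 6, and those who stop later with worsening not yet confirmed and no MRI activity after Month 6. Under a label other than lack of efficacy they leave the mFAS. Under that label they are failures.

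Each removal raises the NEDA-3 proportion by about 0.8 points, given 80 successes among 100. The count cannot be derived from the documents, and the 15% allowance does not make any particular number likely, because it covers all drop-out. Nor do the documents show that the mFAS as a whole is biased upward: the same rule keeps early stoppers with recorded activity and drops those without, which pulls the other way. What is established is a label-dependent exclusion that acts in one direction. It merits correction before lock, and the estimand does not need to be redesigned.

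**What to change.** Before database lock, state in SAP 1.2.1, 2.2, 2.5.1 and 2.5.3 (and in 2.5.4, which repeats the exclusion) that the following is non-response and stays in the mFAS: death, or discontinuation before Month 18 with a recorded reason of lack of efficacy, disease progression or MS relapse. A switch to another MS therapy belongs in this group only where the recorded reason or indication is disease activity. A switch after stopping for an adverse event, poor tolerability or convenience should not count as failure.

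Add a table of mFAS exclusions by recorded reason and by timing relative to Month 6, so that a reader can see how many participants the rule touches.

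The cost is some SAP wording, one table and a short pre-lock review of the disposition and concomitant-medication records, which are already collected. The NEDA-3 estimate may come out slightly lower. No visit, assessment or treatment rule changes.

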- Potential for additional efficacy and safety assessments that will be evaluated during the optional 12-month open-label extension for up to 30 months
- An Optional Biomarker Consent for those participants who opt into additional biomarker sample analysis provided from cerebral spinal fluid (CSF)
- As applicable, Pregnancy Outcomes Reporting Consent for female subjects who took study treatment
- As applicable, Pregnancy Outcomes Reporting Consent for the female partners of male participants who took study treatment

Women of childbearing potential must be informed that taking the study treatment may involve unknown risks to the fetus if pregnancy were to occur during the study and agree that in order to participate in the study they must adhere to the contraception requirements.

A copy of the approved version of all consent forms must be provided to Novartis after IRB/IEC approval.

Participants might be asked to complete an optional questionnaire to provide feedback on their clinical trial experience.

As per [Section 4.6](#), during a Public Health emergency as declared by Local or Regional authorities i.e. pandemic, epidemic or natural disaster, that may challenge the ability to obtain a standard written informed consent due to limits that prevent an on-site visit, Investigator may conduct the informed consent discussion remotely (e.g. telephone, videoconference) if allowable by a local Health Authority.

Guidance issued by local regulatory bodies on this aspect prevail and must be implemented and appropriately documented (e.g. the presence of an impartial witness, sign/dating separate ICFs by trial participant and person obtaining informed consent, etc.).

8 Assessment schedule and assessments

The Assessment Schedule ([Table 8-1](#)) lists all of the assessments when they are performed. All data obtained from these assessments must be supported in the participant's source documentation.

Participants should be seen for all visits/assessments as outlined in the assessment schedule ([Table 8-1](#)) or as close to the designated day/time as possible. Missed or rescheduled visits should not lead to automatic discontinuation.

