9.1.2 Discontinuation from study

Discontinuation from study is when the participant permanently stops receiving the study treatment, and further protocol-required assessments or follow-up, for any reason.

If the participant agrees, a final evaluation at the time of the participant's study discontinuation should be made as detailed in the assessment table (refer to [Section 8](#)).

Discontinued patients will not be replaced in this trial.

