**Table 2 Month 18 interim analysis data cut-off for different participant scenarios**

Participant scenario	Cut-off	Participant data included in Month 18 interim analysis (primary analysis)
Completed Month 18 visit	Date of Month 18 visit + 7 days (inclusive)	All available data up to the date of the Month 18 visit + 7 days (inclusive)*
Did not complete Month 18 visit		
Discontinued study prior to Month 18 visit	None	All available data
Did not discontinue study prior to Month 18 visit	Date of next scheduled visit after Month 18 (exclusive)	All available data up to the date of the next scheduled visit (including home visit) after Month 18 (exclusive).** If the next scheduled visit after Month 18 has not been completed, all available data is used.

\* Including data such as adverse events, medications, non-drug therapies/procedures, protocol deviations and relapses that started prior to or on the date of the Month 18 visit + 7 days.

\*\* Including data such as adverse events, medications, non-drug therapies/procedures, protocol deviations and relapses that started prior to the date of the next scheduled visit (including home visit) after Month 18.

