**Table 7 Criteria for clinical disability progression based on change from Month 6 in EDSS (global assessment scale)**

EDSS at Month 6	Clinical disability progression criterion
0	≥ +1.5
1 to 5	≥ +1
≥5.5	≥ +0.5

- MRI activity-free is defined as no Gd+ lesions on any MRI scan (scheduled or unscheduled) after Month 6, or new/enlarging T2 lesions compared to Month 6 on any MRI scan (scheduled or unscheduled) after Month 6.

The primary estimand is described by the following attributes:

- **Population:** Defined through appropriate inclusion/exclusion criteria to reflect the targeted population. Young adult and very early RRMS (defined as within 6 months of diagnosis of clinically definite RRMS) patients that are DMT treatment naïve.

- **Variable:** NEDA-3 (relapse-free, clinical disability progression-free, MRI activity-free) in Months 6 to 18 (yes/no)
- **Treatment of interest:** An initial dose regimen consisting of doses administered at Baseline/Week 0 (Day 1), followed by Week 1 (Day 7), Week 2 (Day 14), and then every month thereafter, beginning at Week 4 (Month 1) until Month 18. All doses of ofatumumab will be given subcutaneously via an auto-injector at a dose of 20 mg. Healthy controls will be used for comparison purposes and will not receive study treatment.
- **Intercurrent event:** Treatment discontinuation due to lack of efficacy or death
- **Summary measure:** Proportion of participants achieving NEDA-3 in Months 6 to 18

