#### 5.6 Ofatumumab dose dates during open-label treatment phase and open-label extension period

The date of the last dose of ofatumumab during the open-label treatment phase and the date of the first dose of ofatumumab during the open-label extension period will be determined according to the following three participant scenarios.

1. Completed Month 18 visit and continued into open-label extension period
  - a. Last dose date of ofatumumab during open-label treatment phase is last dose date < Month 18 visit date
  - b. First dose date of ofatumumab during open-label extension period is first dose date  $\geq$  Month 18 visit date
2. Completed Month 18 visit and did not continue into open-label extension period
  - a. Last dose date of ofatumumab during open-label treatment phase is last dose date  $\leq$  Month 18 visit date
3. Did not complete Month 18 visit
  - a. Last dose date of ofatumumab during open-label treatment phase is last dose date  $\leq$  Month 18 interim analysis data cut-off date
  - b. First dose date of ofatumumab during open-label extension period is first dose date > Month 18 interim analysis data cut-off date

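### The mFAS missing-assessment exclusion covers only Month 18 completers, so a participant still on ofatumumab who misses the Month 18 visit stays in the primary analysis and counts as NEDA-3 yes by default

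*SAP*

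**What the plan says.** **Analysis set.** SAP 2.2 defines the mFAS as the FAS minus two groups, named in the words "discontinued treatment prematurely prior to Month 18 for reasons other than lack of efficacy or death, or those who completed their Month 18 visit". The second group is removed only where a relapse, EDSS or MRI assessment at Month 6, 12 or 18 is absent. Both exclusions are lifted if disease activity was shown. SAP 2.5.3 and 2.5.4 repeat the same two branches, and the exclusion table in SAP 5.5 only refers back to 2.2. NEDA clinical and NEDA radiological take over the rule through SAP 2.6.3 and 2.6.4.

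**A third state.** Under participants who did not complete the Month 18 visit, SAP Table 2 has a row for "Did not discontinue study prior to Month 18 visit", with its own data cut-off. SAP 5.6 has a scenario "Did not complete Month 18 visit", and its item 3b assigns a first extension dose after the cut-off. Protocol Section 8 says "Missed or rescheduled visits should not lead to automatic discontinuation".

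**Endpoint.** Under SAP 2.5.1 each component is met when no event is recorded. The MRI component, for example, requires "no Gd+ lesions on any MRI scan (scheduled or unscheduled) after Month 6" and no new or enlarging T2 lesions compared with Month 6. It does not say that a Month 18 scan must exist.

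**Protocol.** Sections 12.4.3 and 12.4.4 specify an observed-case (completer) approach for the primary endpoint.

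**The concern.** The missing-assessment exclusion depends on the Month 18 visit having been completed. That condition separates two similar participants in the wrong direction. One attends Month 18 but has no MRI, shows no activity, and is removed. The other, still on treatment, misses the whole visit, shows no activity on earlier assessments, and is kept. The second has less information about Months 6 to 18 than the first.

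The missing visit matters for the outcome. The Month 18 scan is the last look for lesions in the endpoint period. SAP 2.5.1 also accepts a single Month 18 EDSS as confirmed progression. With scheduled EDSS at Months 12 and 18 (SAP Table 3), a worsening first seen at Month 12 would ordinarily be confirmed at Month 18. Without that visit these events may go unseen, and the participant passes every component.

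This is a single-arm estimation study with no hypothesis test (SAP 5.4.1). The primary proportion and its exact interval are the main result, so the rule for who counts and how should be complete before lock.

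**Working it through.** **Step 1. Apply the rule to the uncovered participant.** Take an ofatumumab participant who is still on treatment, did not complete Month 18 and has no recorded activity.

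- First exclusion (SAP 2.2): requires stopping treatment before Month 18. Not met.
- Second exclusion: applies to "those who completed their Month 18 visit but missed relapse/EDSS/MRI (Gd+ or" the T2 equivalent) at Month 6, 12 or 18. Not met, because the visit was not completed.
- Lack of efficacy or death (SAP 2.5.3): not met.
- Result: stays in the mFAS. With no confirmed relapse, no EDSS progression and no lesion on any available scan after Month 6, SAP 2.5.1 gives NEDA-3 yes.

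Study drop-outs are not part of the gap. Protocol 9.1.2 states "Discontinuation from study is when the participant permanently stops receiving the study treatment", so they fall under the treatment-stopping branches.

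**Step 2. Compare with the other planned analyses.** The supplementary completer analysis (SAP 2.5.6) needs completed Month 6 and Month 18 visits and leaves this participant out. NRI (SAP 2.5.6 and 5.1.3.3) scores No when the set of assessments is incomplete. The protocol's completer approach would also leave the participant out. Only the mFAS rule lets the missing visit pass.

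**Step 3. Reproduce the planning figures (SAP 3.1).** The half-width is 1.96 × √(p(1 − p)/100).

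- p = 0.80: 1.96 × √0.0016 = 7.84%, stated as 7.8%.
- p = 0.85: 1.96 × √0.001275 = 7.00%, stated as 7.0%.
- Enrolment: 100/0.85 = 117.6, rounded up to 118.

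Both half-widths are normal approximations. They serve here as a scale.

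**Step 4. Size the effect.** Let k be the number of such participants without recorded activity. The documents do not give k, so 1 to 10 is an assumed range. Take 100 others, x of whom have NEDA-3.

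- Counted yes: (x + k)/(100 + k)
- Excluded: x/100
- Difference: [k/(100 + k)] × (1 − x/100)

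Example for x = 80, k = 5: (5/105) × 0.20 = 0.0095, or 1.0 point.

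| x | k | Counted yes (exact 95% CI) | Excluded (exact 95% CI) | Difference, points |
|---|---|---|---|---|
| 80 | 1 | 81/101 = 80.2% (71.1–87.5) | 80.0% (70.8–87.3) | 0.2 |
| 80 | 3 | 83/103 = 80.6% (71.6–87.7) | 80.0% | 0.6 |
| 80 | 5 | 85/105 = 81.0% (72.1–88.0) | 80.0% | 1.0 |
| 80 | 10 | 90/110 = 81.8% (73.3–88.5) | 80.0% | 1.8 |
| 85 | 3 | 88/103 = 85.4% (77.1–91.6) | 85.0% (76.5–91.4) | 0.4 |
| 85 | 5 | 90/105 = 85.7% (77.5–91.8) | 85.0% | 0.7 |
| 85 | 10 | 95/110 = 86.4% (78.5–92.2) | 85.0% | 1.4 |

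The difference is positive whenever the proportion among the others is below 100%.

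**The case against.** **No passage says that missing data count as yes.** True. The yes follows from applying definitions that look only for recorded events. No mFAS rule prevents it.

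**The group may be empty.** SAP 2.1 and 2.1.1 describe ofatumumab participants at the primary analysis as having completed Month 18 or stopped treatment. The Table 2 row is keyed to leaving the study, not treatment, and the table also serves healthy controls. Under Protocol 9.1.1 a participant who stops treatment is not withdrawn from the study, so that row can hold people whom the first exclusion already removes. For those not extending, Month 18 is the mandatory end-of-study visit (Protocol 9.3). For those extending, it is when re-consent and dispensing take place. This supports a small number but does not close the gap: SAP 5.6 item 3b concerns ofatumumab dosing and allows a first extension dose without a completed Month 18 visit.

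**Month 18 data may still exist.** The Month 18 windows in SAP Tables 3 and 6 run from day 451 to the cut-off day and take unscheduled assessments. For this row of Table 2 the cut-off is set by the next scheduled visit. A late EDSS or MRI can therefore fill the gap, and any activity it shows makes the participant a non-responder. This stands and narrows the group further.

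**A stronger reading.** A reader might infer that the SAP contradicts itself, because 2.5.3 ends by saying "the rest of the participants had disease activities in Months 6 to 18" and scores them as non-response. On that reading the spread would be yes against no: 80.6% against 77.7% (80/103) for 3 participants, and 81.0% against 76.2% (80/105) for 5. The documents do not support it. The clause closes a sentence about discontinuations and missed assessments where activity was not shown, so the remainder it means are those in the same situations who did show activity. Taken literally, it would also score every full completer without activity as a non-responder, leaving no successes.

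**Conclusion.** The gap is real and its effect modest. As written, the mFAS rule keeps a participant on treatment without a completed Month 18 visit, and the component definitions then count that person as NEDA-3 yes if nothing was recorded. Relative to exclusion, the primary proportion rises by about 0.6 points for 3 participants, 1.0 for 5 and 1.8 for 10 at 80% otherwise. At 85% it rises by 0.4, 0.7 and 1.4. All of these are well inside the planned half-width of 7.0 to 7.8 points.

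These sizes rest on an assumed count and on 100 other participants in the mFAS. They also assume that no late assessment supplies Month 18 status. The supplementary completer and NRI analyses already handle the case, so a reader could see part of the effect there. The reason to act is that the primary analysis should not favour the participant with less data, and in an open-label study the rule is better settled before lock than after the cases are visible.

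**What to change.** - **SAP 2.2, 2.5.3 and 2.5.4:** extend the second exclusion to every participant who did not stop treatment before Month 18 but lacks relapse, EDSS or MRI (Gd+ or new/enlarging T2) at Month 6, 12 or 18, judged by the SAP visit windows, whether or not the Month 18 visit was completed. Keep the existing exception for participants who showed disease activity. Keep the named months, so that no new and undefined set of required time points is introduced.
- **SAP 2.5.3, closing clause:** replace the reference to the remaining participants with one to participants retained because disease activity was documented.

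NEDA clinical and NEDA radiological follow through SAP 2.6.3 and 2.6.4 without further edits.

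Exclusion is preferred to scoring No in the primary analysis because it treats this participant like the completer with a missed assessment and agrees with the protocol's completer approach. The supplementary NRI analysis still scores these participants No.

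The cost is wording in three SAP sections before the Month 18 lock, with no new data. The downside is at most a few fewer participants in the mFAS.
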